5.5. Risk Benefit Evaluation for this Study

The administration of tafenoquine may be associated with unforeseen and serious risks.

Full discussions of the potential risks associated with the administration of tafenoquine are detailed in the Investigator's Brochure (60P IB).

No benefit is expected for individual participants participating in this study. Benefits of the study are society-based and related to possible future antimalarial therapies.

Risks to healthy (G6PD normal), participants in this study will be minimized in the following ways:

- Strict adherence to eligibility criteria will be maintained to ensure that only participants who are not at any perceived risk are enrolled in the study;
- The doses have been demonstrated previously to be safe and tolerable in healthy human participants and within predefined exposure limits;
- Close clinical monitoring to ensure the safety and well-being of the study participants including the following:
 - Exclusion of participants with clinically significant abnormalities from participation in the study at screening;
 - Regular measurements of participants' vital signs (blood pressure, pulse rate, sublingual temperature, respiratory rate);
 - Regular assessment of biochemistry and hematological blood parameters (including liver function tests) will be performed at scheduled time points and repeated, if necessary, to ensure appropriate follow-up of any clinically relevant abnormality.
- The total volume of blood drawn from each participant will not exceed 275 mL during the study ([Appendix 3](#)). This volume includes allowance for unscheduled safety laboratory assessments that may be required at the discretion of the PI to ensure participant safety.

5.5.1. Risks/Discomfort to Participants and Precautions to Minimize Risk

Outlined below are anticipated AEs, and a brief description of procedures to ameliorate risks and symptoms. All known risks and precautions described here are explained in detail in the participant information and informed consent form (PIICF).

5.5.1.1. Local Reactions

As the drug is being administered orally, no local reactions are anticipated.

5.5.1.2. Systemic Reactions

Undesirable side effects that have been observed during tafenoquine clinical trials have included the following:

- Blood and lymphatic system disorders, including hemolytic anemia (in patients with G6PD deficiency) and methemoglobinemia.
- Corneal deposits that are fully reversible (within one year). Notably, no treatment-related retinal findings were observed following extended treatment (200 mg x 3 days

loading dose followed by 200 mg/week for 23 weeks) in a Phase 1 clinical safety study (Leary 2009; Study 057).

- GI disorders: nausea, vomiting, abdominal pain and diarrhea.
- Serious hypersensitivity reactions (e.g., angioedema and urticaria) (See also Section 5.5.1.7).

5.5.1.3. Pregnancy

Risks to unborn babies are unknown at this time; pregnant females will be excluded from this study. Female participants should not become pregnant for at least 3 months (5.8 half-lives) after the last dose of IMP. Women of child bearing potential must agree to use an acceptable method of birth control until 90 days following the last dose of IMP.

5.5.1.4. Lactation

Risks to nursing infants are unknown at this time; breastfeeding females will be excluded from this study.

5.5.1.5. Venipuncture

Blood sampling carries a minimal risk of minor discomfort and the possibility of minor bruising at the site of the needle puncture and, rarely, the possibility of infection and radial nerve palsy at the needle puncture site.

5.5.1.6. Ocular Examination and Investigation

Eye examination required administration of topical anesthetic eye drops which stings on initial application. Pupil dilation is required during retinal investigations. This also requires phenylephrine and tropicamide eye drops. All these eye drops are administered during a standard comprehensive eye examination. Blurry vision occurs for up to 4 hours following pupillary dilation. Participants are advised to wear sun glasses and refrain from driving for this period. The risk of angle closure glaucoma is extremely low from pupil dilation. This is further minimized by study procedure that ensures intraocular pressure measurements are taken during ocular examination.

5.5.1.7. Allergic Reaction

As with any IMP administration, no matter what precautions are taken, there is always the risk of serious, or even life-threatening, allergic reaction. Medical emergency equipment is located at the Study Sites. This is available to handle emergencies, such as anaphylaxis, angioedema, bronchospasm, and laryngospasm.

5.5.1.8. Unknown Risks

As with all research, there is the remote possibility of risks that are unknown or that cannot be foreseen based on current information.

5.5.2. Alternatives to this IMP Product or Study

An alternative is not to participate in this study.

5.5.3. Intended Benefit for Participants

This is a study in healthy (G6PD normal) volunteers, thus there is no benefit to the individual or community except the knowledge that the individual's participation has furthered the development of an antimalarial drug.

5.5.4. Risks to the Study Personnel and the Environment

The principal risk in the clinical setting lies in the handling of needles that may be contaminated, the attendant exposure to human pathogens (hepatitis viruses, HIV, and other human pathogens). Adherence to standard operating procedures (SOP) for working with infectious agents and universal precautions will reduce the risk of exposure.

There are no known risks to the environment, other than those associated with the generation of biohazardous waste attendant to drawing blood from humans. All biohazardous waste will be disposed of as stipulated by local, state, and federal regulations and in accordance with study site SOPs.

5.6. Route of Administration, Dosage Regimen, Treatment Period, and Justification

The 600 study participants will be randomized to the tafenoquine or the placebo group in a 1:1 ratio using clinical site as a randomization variable; two groups of 300 participants each will be enrolled in each group.

Each active IMP tablet will contain 100 mg tafenoquine. The dose to be administered orally is 200 mg tafenoquine (2 x 100 mg tablets) per day for three consecutive days (loading doses), followed by another 200 mg dose once per week for the following 51 weeks (beginning post-loading dose Day 10). The placebo group will receive identically-matched double-blind placebo tablets. The IMP tablets will be taken with 180 mL of water but there is no restriction on whether the tablets are taken with or without food.

Safety evaluations will include the following assessments: AE evaluation, physical examination, vital signs, laboratory parameters (hematology, biochemistry, and urinalysis). These will be performed at various time points throughout the study to assess baseline function and any changes from baseline after administration of IMP. Hematology, including methemoglobin assessment, biochemistry and urinalysis will be conducted at Screening, Weeks 4, 12, 24, 52, and 64. Clinical laboratory values indicative of an AE at EOS Week 64 will be repeated during the Follow-up Phase at Weeks 76, 89, 104 until resolution or stabilization.

Previous clinical studies support a recommended dosage tafenoquine regimen for malaria prophylaxis of a loading dose of 200 mg once daily for 3 days before travel to a malarious area, followed by weekly 200 mg maintenance doses while in the malarious area, for a period not exceeding 6 months, and an additional dose of 200 mg at one week of return from travel (60P IB).

In this study tafenoquine will be administered for 12 months to confirm the long term safety of tafenoquine past the 6-month safety window for travelers or military personnel who may be in a malarious area for prolonged periods of time.

5.7. Compliance Statement

The study will be conducted according to the protocol and in compliance with International Conference on Harmonization (ICH) Good Clinical Practice (GCP) ([CPMP/ICH/135/95](#)), and Belmont Principles ([Office for Human Research Protections 1979](#)). All identified study personnel will be trained to perform their roles and will carry out their responsibilities in accordance with ICH GCP guideline and Study Site SOPs.

6. STUDY POPULATION

Up to 600 healthy (G6PD normal), adult men and women aged 18 to 55 years (age matched to the [Study 033](#) ADF population) will be enrolled in the study.

Participants will be recruited from the Study Site's approved database of healthy participants, or in response to a general or study specific advertisement to students of local universities or the general community, as approved by the local HREC, IRB and HRPO. All racial groups will be included.

After an initial telephone interview conducted by clinical trial staff has occurred to review background information, screening visits will be scheduled over two days. Potential participants will be invited to come to the Study Site. During this initial screening visit, the potential participant will read the participant information sheet and will be encouraged to ask questions regarding the information detailed therein. Participants willing to be considered for inclusion may sign the consent form during the screening visit, or return to the Study Site at a later stage after further consideration. The participant will be given a signed copy of the consent form for their records. The signed and dated originals will be held on file by the Study Site.

After providing written consent to participate, the participant will be examined by the PI or sub-investigator. A detailed medical history will be obtained and a physical examination (including measurements of vital signs and basic ophthalmic testing) will be performed. Blood and urine samples will be collected for safety and eligibility assessments. The participants will be fully informed of the nature of the study at this time, and advised of the requirement to repeat some screening tests as indicated (e.g. see [Section 1 Study Schedule of Events](#)) prior to IMP administration.

Eligibility for enrollment will be based on the inclusion and exclusion criteria described below. Participants that fail to meet all eligibility criteria will be excluded from enrollment into the study. The PI or designee will review the screening data and document if a subject meets all of the criteria for enrollment. The PI may also discuss eligibility of a participant with the Local Medical Monitor (LMM).

6.1. Inclusion Criteria

Participants eligible for inclusion in this study must fulfill all of the following criteria:

1. Completion of the written informed consent process (signed).
2. Male or female age 18 to 55 years inclusive, in good health as assessed by the investigator.
3. Normal G6PD enzyme activity levels as defined by the parameters of the specific G6PD test employed at the local laboratory.
4. Negative HBsAg and HCV, HIV-1, HIV-2 antibody screen at the screening visit.
5. Negative serum pregnancy test.
6. Women of child bearing potential must agree to use an acceptable method of contraception from the time of the first administration of the IMP until 12 weeks following administration of the IMP or have undergone a sterilization procedure or are post menopausal. Acceptable birth control methods include:

- a. Oral contraceptives (combination estrogen/progesterone pills), injectable progesterone or subdermal implants (commenced at least 14 days prior to IMP administration to the female participant)
- b. A medically prescribed topically applied transdermal contraceptive patch (commenced at least 14 days prior to IMP administration to the female participant);
- c. Intrauterine device or intrauterine system;
- d. Partner uses condom with spermicide;
- e. Male partner has had a vasectomy (more than 3 months previously)
- f. True abstinence: when this is in line with the preferred and usual lifestyle of the participant. Periodic abstinence (e.g., calendar, ovulation, symptothermal, post-ovulation methods) and withdrawal are not acceptable methods of contraception. Abstinent participants (in consultation with their partners) have to agree to use one of the above-mentioned contraceptive methods, if they start sexual relationships during the study and for up to 90 days after the last dose of study drug.

Acceptable sterilization procedures include:

- g. Essure® sterilization;
 - h. Bilateral tubal ligation;
 - i. Hysterectomy;
 - j. Bilateral oophorectomy; or,
 - k. Be postmenopausal with amenorrhea for at least one year prior to screening and confirmed by a serum FSH test at screening.
7. Willing and able to comply with all scheduled visits, treatment plan, laboratory tests, and other study procedures.
 8. Agree to stay in contact with the study site for the duration of the study and up to 2 weeks following the EOS visit (Week 64), provide updated contact information as necessary, and have no current plans to move away from the study area for the duration of the study.

6.2. Exclusion Criteria

Participants fulfilling any of the following criteria are not eligible for inclusion in this study:

1. History of allergy or intolerance to tafenoquine, primaquine or any excipients.
2. History of thalassemia or current or past history of methemoglobinemia, methemoglobin >2% at screening, or hemolytic anemia.
3. Participants with a history of previous eye surgery, is currently using prescription eye drops or has evidence of corneal or retinal abnormalities identified in Screening ophthalmological examination, or by the investigator following review of examination including but not limited to:
 - a. BCVA (bilateral) at Screening of <72 letters in either eye;
 - b. Eye disease that could compromise assessment of BCVA or imaging of the posterior pole by fundus photography, or SD-OCT, qFAF or is likely to require intervention during the study period (e.g., cataract, glaucoma with documented visual field loss, ischemic optic neuropathy, any inherited retinal disease, nystagmus and any other retinal abnormality or ocular motor disturbance);
 - c. History of retinal vascular disease, retinal detachment, diabetic retinopathy, inflammatory disease, central serious chorioretinopathy, color vision impairment

-
- (up to 5% of male population), amblyopia or other retinal disease that may affect posterior retinal function or architecture;
- d. Vitreoretinal interface disorders (e.g. epiretinal membrane, vitreomacular traction) that may affect posterior retinal function or architecture;
 - e. History of intraocular surgery;
 - f. History of cataract extraction;
 - g. History of retinal laser photocoagulation;
 - h. History of glaucoma shunt or laser treatment;
 - i. History of corneal refractive surgery;
 - j. History of high myopia (defined as equal to, or worse than, -8.00 diopters) as well as those with greater than 3 diopters of astigmatism;
 - k. Anterior, intermediate or posterior uveitis (active or history of) or history of significant intraocular infectious disease (e.g., endophthalmitis is not acceptable to include) or another active inflammatory disease;
 - l. An SD-OCT CSF thickness of <222 μm or >318 μm ([Appendix 4](#)).
4. Participants who have recently taken part in, or plan to take part in, any activities or been exposed to conditions which may affect their eyesight (e.g., scuba diving, high altitudes, sun gazing, laser exposure, or ultraviolet [UV] light).
 5. Participants whose job performance may be affected by participation in the study (e.g., need to wear night-vision goggles).
 6. Participants who, in the opinion of the investigator, do not have the ability to complete the study (e.g. attend all study visits) or to have necessary study investigations performed (e.g. unable to have complete ophthalmic examination as specified in the protocol).
 7. Those having received another IMP within 30 days or five half-lives (whichever is longer), of study start.
 8. Those having previously received hydroxychloroquine for skin conditions or rheumatological diseases, chloroquine for malaria, tamoxifen, amiodarone or other drugs that may affect the optic nerve/retina/cornea within 30 days or 5 half-lives (whichever is longer) of study start. There are no travel restrictions, but the choice of concurrent anti-malarial must be atovaquone-proguanil if the participant chooses to take a registered antimalarial drug while travelling.
 9. Have any of the following, based on DSM-5 criteria as assessed using the MINI:
 - a. History of psychotic disorders or current psychotic symptoms (hallucinations, delusions, or grossly disorganized thinking or behavior)
 - b. Current (past year) suicide behavior disorder or current (past month) suicidality
 - c. or any other current diagnosis of psychiatric disorders . Note: Past history (not diagnosed as current) of a psychiatric disorder within the past year will be referred to the Study Psychiatrist or Psychologist for further evaluation and determination of whether the subject should be excluded from participation in the study. Subjects with a stable past psychiatric disorder, as determined after evaluation by the Study Psychiatrist or Psychologist, may be admitted to the study. If the subject is excluded; the person in question will be referred to their General Practitioner (GP). A subject admitted to the study with a psychiatric history, either self-reported or discovered by M.I.N.I will have their past illness documented in the

medical history eCRF and any current psychiatric medication documented as a concomitant medication.

10. Urine drug screen positive for cocaine, methamphetamine, amphetamines, methamphetamines, barbiturates, benzodiazepines, methadone, opiates, phencyclidine, or tetrahydrocannabinols. Note urine drug screen positive for tricyclic antidepressants or benzodiazepines is allowed if participant reports prescription use for a stable medical/psychiatric condition. Limited use of prescription or non-prescription medications containing codeine and not believed to affect participant safety or the overall results of the study, may be permitted on a case-by-case basis following approval by the Investigator (in consultation with the Medical Monitor, as appropriate).
11. Blood alcohol level > 0.0 determined using an alcohol breathalyzer. Note on interviewing the participant, the investigator may allow enrolment if they are satisfied the participant does not have alcohol dependence and can successfully complete the study protocol. A second blood alcohol test level > 0.0 at Week 1, Day 1 (Visit 2) would constitute grounds for exclusion of the participant.
12. Participants with medical history that might compromise their ability to comply with the protocol.
13. History of cancer (excluding basal or squamous cell carcinomas).
14. Have a clinically significant ECG as determined by the investigator or QTc interval corrected for heart rate using the Fridericia formula ($QTcF$) > 450 msec.
15. Hemoglobin, platelet counts or neutrophil counts outside the local laboratory reference range and are judged by the investigator to be clinically significant. A laboratory test may be repeated once during screening at the discretion of the Investigator. A subject with a hematology result outside the local laboratory reference range may be admitted to the study if the result is judged as not clinically significant.
16. Alanine aminotransferase (ALT), aspartate aminotransferase (AST), total or direct bilirubin, gamma glutamyl transferase (GGT) or creatinine > 1.5 times the upper limit of normal (ULN) and are judged by the investigator to be clinically significant. A laboratory test may be repeated once during screening at the discretion of the. If other biochemistry tests fall outside the local laboratory reference range, the subject may be admitted to the study if the out-of-range result is judged as not clinically significant by the investigator.

For other eligibility criteria considerations, the investigator is referred to the IB (60P IB) or current US Prescribing Information for detailed information regarding warnings, precautions, contraindications, AEs, and other significant data pertaining to the use of tafenoquine. The medical monitor should be contacted if the investigator has any questions regarding subject eligibility.

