12.2.2. Subject Demographics and Baseline Characteristics

The participant disposition and demographic data (including age, weight, height and race/ethnicity) will be tabulated by group and overall for both treatment groups. Study completion, study withdrawals, exclusions and violations will be listed and the reasons for withdrawal, exclusions and violations will be listed.

Data for background and demographic variables will be listed by treatment group and participant. Descriptive statistics will be provided by treatment group.

Medical, surgical and social history, current medical conditions results of laboratory screening tests, drug tests and any other relevant baseline information (including serology results, alcohol breathalyzer test, urine drug screen, and G6PD testing and pregnancy test results) will be listed by treatment group and participant.

Previous and concomitant medication taken at any stage from 4 weeks prior to dosing and during the study period will be listed per treatment group.

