12.2.3.2. Secondary Endpoints

The incidence of AEs, SAEs, laboratory parameters and vital signs will be summarized descriptively by treatment group and study visit. The AEs will be summarized at $\geq 1\%$ (common) and $\geq 10\%$ (very common) level.

For the secondary safety endpoints, the proportion of participants with an abnormal change or new abnormal change will be compared by a Fisher's exact test between tafenoquine and placebo. The 95% CI of the abnormality rate will be summarized by Clopper Pearson Exact methodology. A logistic regression will be used to compare the risk of having the abnormality (odds ratio and 95% CI) between tafenoquine and placebo. These analysis methods will be applied to the following secondary safety endpoints: proportion of participants with abnormal changes from baseline observed on qFAF, proportion of participants with corneal deposits from slit lamp examination of the corneal epithelium, proportion of participants with new abnormal changes from baseline observed with color retinal digital photography (conventional and wide field), proportion of participants with new abnormal changes from baseline observed with microperimetry, proportion of participants with any new anomaly on the backlit ETDRS chart, proportion of participants with any clinically significant change in ETDRS BCVA (defined as ≥ 15 letter change [≥ 3 lines] of change in ETDRS BCVA at 4 meters), proportion of participants who develop a new color deficiency using the FM-100 hue test, proportion of participants who develop a loss of 0.12 or greater logCS on the Mars letter contrast sensitivity test, proportion of participants who develop a new identified psychiatric disorder, and proportion of participants with an AE of dizziness or vertigo and severity as assessed by the DHI.

For time to event safety endpoint, a log-rank test will be used to compare the time to onset/resolution of the event between tafenoquine and placebo. Cox regression will be used to compare the risk of having the safety endpoint (hazard ratio and 95% CI) between tafenoquine and placebo. The survival analysis methods will be applied to the endpoints of time to onset, and time to resolution of corneal deposits after treatment cessation.

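### Psychiatric history is recorded at entry but not used in the planned comparison of new psychiatric disorder; a history-stratified analysis would be a small, cheap gain

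*Combined protocol and SAP*

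**What the plan says.** Section 6.2, criterion 9, excludes any current psychiatric diagnosis and anyone with "History of psychotic disorders or current psychotic symptoms". It leaves room for past, stable, non-psychotic illness: "Subjects with a stable past psychiatric disorder, as determined after evaluation by the Study Psychiatrist or Psychologist, may be admitted to the study". The information is kept: "A subject admitted to the study with a psychiatric history, either self-reported or discovered by M.I.N.I will have their past illness documented". It is held on the eCRF page for medical history, and psychiatric drugs in use are entered as concomitant medication.

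Section 7.4 randomises 1:1 in permuted blocks, with clinical site as the only randomisation variable.

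Section 12.2.3.2 sets one method for all binary secondary safety endpoints. The proportion with an abnormality "will be compared by a Fisher's exact test between tafenoquine and placebo", with Clopper-Pearson limits for the rates. In addition: "A logistic regression will be used to compare the risk of having the abnormality (odds ratio and 95% CI) between tafenoquine and placebo". No covariates are given. Both methods apply to the "proportion of participants who develop a new identified psychiatric disorder".

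Under section 12.2.2, medical history "will be listed by treatment group and participant". No analysis by psychiatric history appears elsewhere in the text. Section 12.2.1 leaves further detail to a SAP to be finalised before unblinding.

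**The concern.** A past psychiatric disorder is a likely predictor of a psychiatric diagnosis over the next year. The trial chooses to admit such people and records the variable before dosing, yet no described analysis uses it. Three things follow.

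- Some efficiency is lost in the comparison of arms.
- If the arms differ by chance in the share with a history, the crude risk difference moves with that imbalance, and no pre-specified analysis is available to show by how much.
- If an excess appears on tafenoquine, the plan gives only listings from which to see whether it lies in people with a past disorder, without one, or both.

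The question is not idle. Section 4.2 makes psychiatric change a secondary objective. The background section on earlier trials reports more psychiatric adverse events on tafenoquine than on placebo and explains this partly by the risk profile of the deployed population.

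A linked gap is the event definition. Section 5.2.2 speaks of developing a disorder, while section 12.2.3.2 speaks of a new, or a new and current, disorder. For secondary eye endpoints, section 12.1 says that worsening of a pre-existing abnormality can count. There is no matching rule for psychiatric endpoints, so it is open whether recurrence of a documented past disorder is an event.

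**Working it through.** **The plan's own figures.** There is no sample size, power or event rate for the psychiatric endpoint. The figures in section 12.1 concern the ophthalmic primary endpoint, and they reproduce:

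- Power at 300 per arm, 1% in both arms and a 2.5-point margin: SE = √(2 × 0.01 × 0.99/300) = 0.00812, and Φ(0.025/0.00812 − 1.96) = 86.8% (stated 86%).
- Chance of at least one event: 1 − 0.99^300 = 95.1% (stated 95%).

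Neither bears on this point, so what follows rests on assumptions.

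**Formulas.** Let h be the share with a history, p0 and p1 the risks without and with it, p = h·p1 + (1 − h)·p0, and n = 300 per arm.

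- Proportion of variance removed by stratifying: R² = h(1 − h)(p1 − p0)² / [p(1 − p)]. The SE falls by 1 − √(1 − R²). The equivalent gain is 600 × [1/(1 − R²) − 1] participants.
- Shift in the crude risk difference from a 1.96-SD chance imbalance in history: 1.96 × √(2h(1 − h)/n) × (p1 − p0).
- Half-width of the crude 95% CI: 1.96 × √(2p(1 − p)/n).

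**Grid A** (h 5–20%, p0 1–5%, risk ratio for history 2–5). R² runs from 0.05% to 7.8%, so the SE falls by 0.02% to 4.0%, worth about 0 to 51 participants. In 21 of the 27 combinations the SE falls by less than 1%. Middle case, h = 0.10, p0 = 0.03, p1 = 0.09: p = 0.036; R² = 0.09 × 0.0036/(0.036 × 0.964) = 0.93%; the SE falls by 0.47%, worth about 6 participants.

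**Grid B** (h 10–30%, p0 3–5%, p1 10–30%), more favourable to adjustment:

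| h | p0 | p1 | p | R² | Imbalance shift (points) | CI half-width (points) |
|---|---|---|---|---|---|---|
| 0.10 | 0.05 | 0.10 | 0.055 | 0.4% | 0.24 | 3.65 |
| 0.20 | 0.03 | 0.15 | 0.054 | 4.5% | 0.77 | 3.62 |
| 0.30 | 0.03 | 0.30 | 0.111 | 15.5% | 1.98 | 5.03 |

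Over the whole of grid B, R² is 0.4–15.5%, the shift 0.24–2.0 points and the half-width 3.0–5.3 points. Crossing the extremes of the two grids (h = 0.30, p0 = 0.01, p1 = 0.30) would give R² = 0.21 × 0.0841/(0.097 × 0.903) = 20%, but that needs a thirtyfold risk ratio in screened volunteers.

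**Tests and odds ratio.** Simulation, 3,000 trials per row, 300 per arm, p0 as the placebo risk without history:

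| h, p0, OR history, OR drug | Fisher | Stratified CMH | Logistic, unadjusted → adjusted | SE of log OR |
|---|---|---|---|---|
| 0.1, 0.03, 3, 2.5 | 65.2% | 71.1% | 69.9% → 70.2% | 0.389 → 0.393 |
| 0.1, 0.05, 5, 2 | 58.5% | 65.7% | 63.4% → 65.3% | 0.298 → 0.306 |
| 0.2, 0.03, 5, 2.5 | 75.2% | 81.6% | 78.1% → 81.1% | 0.327 → 0.336 |
| 0.1, 0.03, 3, 1 (null) | 3.2% | 4.7% | 3.9% → 4.2% | 0.460 → 0.463 |

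The stratified test gains 6 to 7 points over Fisher, but much of that is Fisher's conservatism (type I error 3.2% against a nominal 5%). Adjusting the logistic model adds 0.3 to 3.0 points of power while slightly raising the SE of the log odds ratio. Further runs put the contribution of history itself at about −0.6 to +2.4 points.

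**Within the history stratum.** With h = 5–20% there are 15 to 60 people per arm. For rates of 5–15% the 95% half-width of the risk difference is 8 to 26 points (60 per arm at 5%: 1.96 × √(2 × 0.05 × 0.95/60) = 7.8 points; 15 per arm at 15%: 25.6 points). Power to detect a doubling is 7% to 50%.

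**The case against.** The best case for leaving the plan alone is that randomisation makes the crude comparison unbiased and that its interval already allows for chance imbalance. The endpoint is one of many secondary ones and was not used to size the trial. The admitted group should also be at limited risk: healthy volunteers, no psychotic history, no current diagnosis or suicidality, and specialist evaluation of past-year history. Most psychiatric events listed from earlier trials affected 1 or 2 of 825 people. All of this stands, and it keeps the gain small.

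It is also fair that worsening is caught elsewhere. Section 9.2.7 sends new or worsened disease for specialist evaluation and adverse event recording, and section 12.2.1 counts worsening as treatment-emergent. With the history listings, a descriptive look by history could be pieced together afterwards. That is weaker than a pre-specified table, but it is not nothing.

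A reader might infer more than the documents support:

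- *That the logistic regression contains treatment only.* Section 12.2.3.2 leaves its covariates unspecified, and the SAP could still name them. Only Fisher's test is certainly unadjusted.
- *That first episodes and recurrences are pooled.* The text does not say so; whether a recurrence is new is undefined.
- *That ignoring history biases the comparison.* It does not. The imbalance shift above is a 1-in-20 extreme already covered by the interval.

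**Conclusion.** The point holds in a limited form. The variable is foreseen and collected, and the described analysis leaves it out. Naming a history-stratified analysis in advance is a specific improvement at almost no cost.

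Its size should not be oversold. With no history share or event rate in the documents, the estimate rests on the assumed grids: a variance reduction for the risk difference of about 0–15%, usually a few percent or less, and no reduction in the SE of the log odds ratio. A reader might take this as a substantial loss of precision, but the upper end needs 30% of participants with a history and a tenfold risk ratio. Nor would a by-history table settle the drug's effect in people with a past disorder, given half-widths of 8 to 26 points.

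What remains is modest efficiency, protection against chance imbalance, a descriptive table, and a needed rule on recurrence. This is a change to consider, and interpretation is a stronger reason for it than precision.

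**What to change.** In section 12.2.3.2 and the SAP, before unblinding, for the M.I.N.I. disorder and C-SSRS endpoints:

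1. Lead with the tafenoquine-minus-placebo risk difference and 95% CI by Mantel-Haenszel, stratified by psychiatric history at entry (yes/no, from medical history and the Screening M.I.N.I.).
2. Add the same yes/no term to the logistic model, with a penalised or exact fit if events are sparse.
3. Tabulate events by arm within each history stratum, descriptively and without a stratum-level test.
4. Keep Fisher's exact test as a sensitivity analysis.
5. State whether recurrence of a documented past disorder counts as new, and use the same wording in sections 5.2.2 and 12.2.3.2.

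The cost is a few sentences and one extra table; no new data or visits are needed. The downside is that the stratum intervals will be wide and one stratum may have few events. The Mantel-Haenszel risk difference tolerates this, and the table should be labelled descriptive.
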